(Tzefos 2009, AHRP reference guide) Additionally, fesoterodine has been compared to tolterodine, and may show greater efficacy. (Tzefos 2009) In fact, fesoterodine tends to have low incidence of dry mouth, and moderate incidence of constipation compared to other anti-muscarinics, making it a well-tolerated and appropriate first choice for most patients.(Ellsworth 2014) Low CNS penetration may also potentiate fewer CNS side effects.(Ellsworth2014) Additionally, our previously presented data on the potential positive effects of anticholinergic medication on physical activity was collected using fesoterodine, so there is a precedent for using this anticholinergic in a study examining changes in activity and sedentary behavior. Therefore, fesoterodine, the drug used in this study, is an appropriate medication for routine and standard care of overactive bladder. Fesoterodine is being supplied by Pfizer for the use of this study. As part of routine clinical care at the urogynecology clinics of the University of Pennsylvania Health System, all patients receive a pelvic exam, measurement of post-void residual by bladder ultrasound, and administration of four urinary questionnaires as part of evaluation of urinary symptoms. The OABq-SF and the UDI-6 will be used to screen patients. Inclusion Criteria: adults aged 65 or older, urinary urgency of quite a bit severity or more on the Overactive Bladder Questionnaire-Short Form (OABq-SF),50 who are eligible for pharmacologic therapy for overactive bladder Exclusion Criteria: predominant stress incontinence (on UDI-6), current/recent use (6 m) or contraindication to anti-cholinergic medication, severe voiding difficulties, men on 5-alpha reductase inhibitors, severe neurologic disease, recent anti-incontinence or prolapse surgery, other urinary tract conditions such as calculus or recurrent UTI. Recruitment/Retention Experience: The urogynecology/urology clinics of the Hospital of University of Pennsylvania are high volume referral clinics staffed by four urogynecologists and one urologist. We see 125 female and 50 male patients with OAB per month with eligibility:participation ratio of 1.5:1 in clinical trials.42, 48, 51 In recent trials, 50% of recruited adults were Caucasian and 45% African-American. We anticipate that the female:male ratio will be 2:1. Recruitment : Pre-screening will occur at a patients routine visit, or via chart review following clinical care. If a patient appears to be eligible, they will be referred to the study coordinator to schedule a baseline visit. Patients of urogynecology or other referring geriatrics/urology/primary care practices may also self-refer for participation, as long as their medical records are available for eligibility determination. Baseline visit: At this visit, the trained coordinator will obtain informed consent, administer physical activity and other questionnaires (see Instrument and Testing Schedule below). Routine pre-treatment counseling on medical treatment, as well as counseling on additional non-medical (biofeedback, behavioral strategies, pelvic floor muscle training) and interventional treatments (neuromodulation), will also be provided. Then the coordinator will administer the Preference instrument on a bidirectional scale with 0 being undecided, and either extreme (5 or -5) being a strong preference for that particular treatment. The Short Physical Performance Battery (SPPB) test will also be performed with the oversight of trained personnel for safety. Accelerometers and instructions for wearing the accelerometer will be provided at that time. The monitor will be retrieved from the patient by a study coordinator or investigator 1 week later. Intervention: All subjects (irrespective of preference) will receive a 90-day supply of open label fesoterodine 4 mg per day. They will start medication 1 week after the baseline visit. After 4 weeks of treatment, dose may be increased to 8 mg over the telephone based on symptom report. This dosing regimen is direct alignment with clinical care. Change of prescription to another anti-cholinergic may occur during the study period, if determined necessary by the physician. Criteria that would warrant stopping fesoterodine include: - inability to tolerate common side effects, including dry mouth, dry eyes, and constipation - lack of satisfactory urinary symptom control on the highest dose of fesoterodine - immediate withdrawal in case of life-threatening side effects (uncommon, including angina, angioedema, diverticulitis, gastroenteritis, heat prostration, hypersensitivity reactions, irritable bowel syndrome, QT prolongation) Once withdrawn from fesoterodine, managing physicians would use their clinical judgment to switch the patient to another anti-cholinergic medication or switch to another class of medication (beta 3 agonist, or mirabegron). These patients would continue to be followed until after the 8 week follow-up visit, as the statistical plan will involve intention-to-treat analysis. The patients will continue to participate in the 8 week follow-up visit (including questionnaires and SPPB), regardless of whether or not they were switched to another medication. All adults will receive printed educational material on fluid modification, behavioral strategies, and Kegel exercises. 8 week follow up visit: One week prior, the study coordinator will once again provide subjects with accelerometers and instructions for wearing the accelerometer. At the 8 week visit, the patient will again complete self-administered physical activity, urinary symptoms, adherence, pill count, and neurocognitive instruments and tests with the oversight of a trained investigator (see Instrument and Testing Schedule below). The monitor will be retrieved from the patient by a study coordinator or investigator at the 8 week follow up visit. Instrument and Testing Schedule BASELINE VISIT: Urinary questionnaires (OABq-SF, UDI-6) Preference: Belief in Medication Questionnaire (BMQ), Bidirectional Visual Analogue Preference scale Physical activity:

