Study visits will typically occur in the subjects home, unless they prefer to come to the office. 1. Recruitment and Enrollment: Following a routine office visit, or upon self-referral and review of records, the patient will be scheduled for a baseline visit with the coordinator, if eligible. Additional pre-screening may occur with the subject via phone. 2. Baseline visit: The study coordinator will finish confirming eligibility via pre-screening questions (if not already completed prior to the visit). Once eligibility is confirmed, subjects will provide consent. Additionally, the subjects will fill out the following questionnaires: Preference: Belief in Medication Questionnaire (BMQ, gold standard), Bidirectional Visual Analogue Preference scale Physical activity: Accelerometer (gold standard), Self-reported questionnaires (IPAQ, CHAMPS) Neurocognitive measures: Questionnaires (Minicog, Falls risk) Urinary: Questionnaires (OABq-SF, UDI-6) Quality of Life: SF-12 Bowels: Questionnaires (Birmingham) Short Physical Performance Testing will be performed with oversight from trained personnel. The study coordinator will provide subjects with accelerometers and instructions for wearing the accelerometer. The monitor will be retrieved from the patient by a study coordinator or investigator a week later. 3. Intervention: All subjects will receive a 90-day supply of open label fesoterodine 4 mg per day, which they will start 1 week after the baseline visit. After 2 weeks, dose may be increased to 8 mg over the telephone based on symptom report. Change of prescription to another anti-cholinergic may occur during the study period, if determined necessary by the physician. See full criteria in previous intervention section above. 4. 8 week follow up visit: At this visit, the patient will complete the following self-administered physical activity, urinary symptoms, adherence, pill count, and neurocognitive instruments and tests: Physical activity: Accelerometer (gold standard), Self-reported questionnaires (IPAQ, CHAMPS) Neurocognitive measures: Questionnaires (Minicog, Falls

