risk), Short Physical Performance Battery Urinary: Questionnaires (OABq-SF, UDI-6) Bowels: Questionnaires (Birmingham) Quality of Life: SF-12 Adherence: Questionnaires (BMQ follow up, MASRI), pill count Patient Global Index of Improvement (PGI-I) form The study coordinator will again provide subjects with accelerometers and instructions for wearing the accelerometer, one week prior to the 8 week visit. The monitor will be retrieved from the patient by a study coordinator or investigator at the 8 week visit. Instrument and Testing Schedule BASELINE VISIT: Preference: Belief in Medication Questionnaire (BMQ, gold standard), Bidirectional Visual Analogue Preference scale Physical activity: Accelerometer (gold standard), Self-reported questionnaires (IPAQ, CHAMPS) Neurocognitive measures: Questionnaires (Mini cog, Falls risk), Short Physical Performance Testing Urinary: Questionnaires (OABq-SF, UDI-6) Quality of Life: SF-12 Bowels: Questionnaires (Birmingham) 8 WEEK FOLLOW-UP VISIT: Physical activity: Accelerometer (gold standard), Self-reported questionnaires (IPAQ, CHAMPS) Neurocognitive measures: Questionnaires (Mini Cog, Falls risk), Short Physical Performance Testing Urinary: Questionnaires (OABq-SF, UDI-6) Bowels: Questionnaires (Birmingham) Quality of Life: SF-12 Adherence: Questionnaires (BMQ follow up, MASRI), pill count Patient Global Index of Improvement (PGI-I) form

The following documents are currently attached to this item:

There are no documents attached for this item.

Deception

Does your project use deception?

No

International Research

Are you conducting research outside of the United States?

No

Analysis Plan

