Analysis Plan Specific Aim 1 and 2: We will evaluate physical activity, adherence, and neurocognitive function before and after treatment to examine changes from baseline to 8 weeks in subjects with and without preference for medication. Concurrent validity, the relationship of the instrument to other similar evaluations, will be measured by comparing IPAQ, and CHAMPS scores to accelerometer data at baseline using the Spearman correlation coefficient and the intraclass correlation coefficient. Specifically, we will compare energy expenditure in MET*min/week (IPAQ) or MET*hour/week (CHAMPS) to that measured by the Actigraph accelerometer over the course of a week. For preference, we will compare subjects scores as indicated on the bidirectional scale to their necessity-harm differential as calculated by the Belief Screen of the BMQ using Spearman correlation coefficient. Contingency analyses tables will be used to determine the sensitivity and specificity of the bidirectional preference scale and the necessity-harm differential (as calculated on the Belief Screen) that best discriminates between those with preference for medication and those without. Discriminant validity, the ability to distinguish between populations, will be determined by comparing mean differences in energy expenditure for each physical activity instrument between responders and non-responders to anticholinergic medication as defined by the PGI-I. We will compare total MET*min/week (IPAQ) or MET*hour/week (CHAMPS), as well as energy spent in sedentary and moderate-to-vigorous physical activities (CHAMPS) between responders and non-responders using Wilcoxon rank sum test. For preference, we will compare the BMQ Belief necessity-harm differential and bidirectional preference scale score using Wilcoxon rank sum test. Responsiveness, the ability of the instruments to detect clinically meaningful change, will be assessed. First, pretreatment energy expenditure and preference will be compared with post-treatment activity and preference scores, respectively, using the t-test. Next, effect size (change in mean score/SD of baseline) and standardized response mean (change in mean score/SD of the change) will be assessed. For both, values of 0.50.7 will be considered moderate responsiveness; 0.81, good; and 1, excellent. We will measure minimum clinically important difference (MCID); specifically, the smallest change in physical activity associated with clinically meaningful change in global rating scale (mean change in energy expenditure in subjects indicating a little better or greater in the global rating scale). Specific Aim 3: We will compare within subject change in physical activity from baseline to 8 weeks using the paired t-test. Improvement in physical activity will be defined as 15% increase in energy expenditure as compared to baseline. The effect of age, comorbidities, baseline activity, severity of cognitive impairment, BMI on physical activity will be examined using regression analysis. We will also compare change in activity, proportion of subjects

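### Aim 2 plans sensitivity and specificity for both preference instruments against a preference status the plan never defines, at a cut chosen in the same subjects

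*Combined protocol and SAP*

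**What the plan says.** The Analysis Plan (Specific Aim 1 and 2, concurrent validity) handles preference in two steps. The first is a Spearman correlation: "we will compare subjects scores as indicated on the bidirectional scale to their necessity-harm differential". The second is a cross-classification: "Contingency analyses tables will be used to determine the sensitivity and specificity of the bidirectional preference scale and the necessity-harm differential", and the sentence ends with the value "that best discriminates between those with preference for medication and those without".

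No section says what puts a subject in the group with preference, and no cut is given for either measure. The Procedures section lists "Preference: Belief in Medication Questionnaire (BMQ, gold standard), Bidirectional Visual Analogue Preference scale". The Instrument and Testing Schedule under Study Design names the same two measures without the gold-standard label. Neither schedule has a third preference item.

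The Baseline visit text describes the "Preference instrument on a bidirectional scale with 0 being undecided, and either extreme (5 or -5) being a strong preference for that particular treatment". All subjects then receive the study drug whatever their preference, so the treatment taken cannot supply the status either. No split sample, cross-validation or optimism correction is planned.

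**The concern.** Sensitivity and specificity need a reference that stands apart from the test. Here both available preference measures are named as tests, and the reference is a status that nothing else in the schedule measures. Whichever of the two is used to assign the status will be scored against itself. The other will be read at the cut that looks best in the data that report it.

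Aim 2 is meant to say which instrument, if any, is useful for measuring preference. Aim 3 then uses the validated instruments to compare adults who prefer medication with those who do not. The Aim 2 adherence comparison and its sample-size statement need the same split. An undefined status therefore affects how these figures can be read, and leaves open how the later groups are formed.

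**Working it through.** The documents give no sensitivity, specificity, cut or precision target on this point, so there is no planned figure to reproduce.

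**Inputs from the documents.** Enrolment is 80, and at least 68 subjects with complete data after 15% loss (80 × 0.85 = 68). Both preference measures are taken at baseline, so the number with both may be nearer 80. The scale runs from −5 to 5 with 0 as undecided. The sample-size text assumes that 50% prefer medication.

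**Assumptions not in the documents.** The latent correlation between the two instruments (0, 0.3, 0.5), normal underlying scores, and an integer differential.

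**Step 1: an instrument against itself.** If status is defined as T > c and the test is T > c, then
- sensitivity = P(T > c | T > c) = 1
- specificity = P(T ≤ c | T ≤ c) = 1

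This holds for any data, including pure noise, and needs no simulation. It is conditional on one of the two instruments supplying the status.

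**Step 2: the other instrument, cut tuned in the same data.** Let J = sensitivity + specificity − 1, with the cut chosen to maximise J. Inflation is the mean apparent J minus the J obtained without tuning.

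Set-up A compares the apparent J with the true J at the cut that was chosen (2,000 trials per one-cut row, 600 per both-cuts row):

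| Tuned | N | Correlation | Apparent J | True J | Inflation |
|---|---|---|---|---|---|
| One cut | 80 | 0 | 0.095 | −0.001 | 0.096 |
| One cut | 80 | 0.3 | 0.247 | 0.170 | 0.077 |
| One cut | 80 | 0.5 | 0.370 | 0.305 | 0.065 |
| One cut | 68 | 0 | 0.108 | 0.000 | 0.108 |
| One cut | 68 | 0.3 | 0.256 | 0.166 | 0.090 |
| One cut | 68 | 0.5 | 0.379 | 0.304 | 0.075 |
| Both cuts | 80 | 0 | 0.276 | 0.002 | 0.274 |
| Both cuts | 80 | 0.3 | 0.459 | 0.203 | 0.256 |
| Both cuts | 80 | 0.5 | 0.601 | 0.361 | 0.240 |

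Set-up B compares tuned cuts with both cuts fixed at > 0 (N = 80, 2,000 trials per setting, cuts leaving at least 10% on each side):
- One cut tuned: 0.09 − 0.00 = 0.09; 0.25 − 0.19 = 0.06; 0.37 − 0.33 = 0.04 (correlations 0, 0.3, 0.5).
- Both cuts tuned: 0.24 − 0.00 = 0.24; 0.42 − 0.19 = 0.23; 0.56 − 0.33 = 0.23.

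**Step 3: per measure.** J is the sum of two measures, so the average inflation of each is half. With one cut tuned at N = 80, 0.04/2 = 2 points to 0.10/2 = 5 points. With both cuts tuned and unrelated instruments, set-up A shows about 63% sensitivity and 65% specificity where the true J is zero.

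**Step 4: set against sampling error.** With 50% preferring medication, 80/2 = 40 subjects carry the sensitivity. At 65%, the 95% half-width is 1.96 × √(0.65 × 0.35 / 40) = 0.148, about 15 points. The one-cut bias is smaller than this, but it always runs in the favourable direction and a confidence interval does not reveal it.

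**The case against.** The plan leaves the reference unstated. It does not say that these two instruments define the status. A reader might infer that one instrument is bound to score 100%/100%. That follows only if one of them alone is the reference; a composite or an adherence-based reference would avoid it, although the plan describes neither. The sentence can also be read as one cross-table that seeks the differential value best separating those who express a preference on the scale. Testing one instrument against a declared other is a legitimate agreement analysis. This objection stands, and it makes the 100% result conditional. It does not supply the missing reference, and on the single-table reading the cut is still tuned in the data that report it.

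A reader might also infer that the figures would be grossly inflated. That needs both cuts to be tuned, which the plan does not say. If the gold-standard label means a fixed reference cut, the inflation is modest.

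Finally, a reader might infer that Aim 2 cannot tell a valid scale from noise. The documents do not support this. The Aim 2 hypothesis and sample size rest on 8-week adherence, measured separately by MASRI and pill count, and the Spearman correlation needs no cut. Neither analysis is circular. Nor do the documents say that the Aim 3 groups will use the data-chosen cut; they give no cut at all.

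**Conclusion.** The point holds in a limited form. As written, the plan asks for sensitivity and specificity of both preference measures, collects no third one, and seeks the best cut without correction. If either instrument supplies the status, its own pair of figures is uninformative by definition.

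The other pair is optimistic. For assumed correlations of 0 to 0.5, J is inflated by about 0.04 to 0.10 at N = 80 (up to 0.11 at N = 68) with one cut tuned, and by about 0.23 to 0.27 if both are tuned. These sizes depend on the assumed correlation and score distributions; the direction of the bias does not.

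The damage is confined to the sensitivity and specificity figures. The correlation and adherence analyses survive, although the adherence groups need the split that the plan leaves undefined. This is a cheap improvement, not a flaw that voids Aim 2.

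**What to change.** Replace the contingency-table sentence with a short rule:

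- **Declare one reference in advance.** The necessity-harm differential is one candidate, with its cut pre-set by the sponsor. A differential > 0 is a proposal here; the documents give no such cut.
- **State which BMQ yields the differential.** The Background attributes the Belief Screen to the Brief Medication Questionnaire, while the visit schedules name the Belief in Medication Questionnaire under the same abbreviation.
- **Pre-set the scale's test cut** at > 0 toward medication, since 0 means undecided. State which sign means medication, and use the same cut for the Aim 2 and Aim 3 groups.
- **Report sensitivity and specificity with 95% CIs for the non-reference instrument only**, and call the result agreement with the BMQ. Drop the self-referenced pair.
- **Use 8-week adherence**, already collected, as the independent criterion for comparing the two instruments.
- **Report any best-discriminating cut as exploratory**, with bootstrap optimism-corrected figures.

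The cost is a few sentences and no new data. The reported figures will be slightly less favourable, and one pair of figures is lost.

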Our primary objective is to show that treatment preference and physical activity can be measured using patient-reported instruments. We also hypothesize that preference for anti-cholinergic medications is associated with higher adherence and improvement in domains relevant to falls in adults with OAB, including urgency, physical activity, and balance. Finally, we plan to show that treatment of urgency urinary incontinence with anti-cholinergic medication does not worsen neurocognitive function relevant to falls. Specifically, the overriding goal of this proposal is to validate patient-reported instruments that measure physical activity and preference for medication in elderly adults with overactive bladder, and examine the effect of treatment on physical activity and risk for falls (fall efficacy) in adults who prefer medication for the treatment of overactive bladder. Specific Aim 1: To determine the construct validity and responsiveness of physical activity instruments in older adults undergoing treatment for overactive bladder. We hypothesize that physical activity levels as measured by questionnaires will correlate with physical activity as measured by accelerometer. We will measure responsiveness of the instruments by comparing change in physical activity levels before and after treatment of OAB. The results will be informative as to which, if any, instrument is useful for measuring physical activity in adults with OAB. Specific Aim 2: To determine the construct validity of an instrument to measure preference for medication in older adults undergoing treatment for overactive bladder. We hypothesize that adults with preference for medication will have higher adherence to treatment at 8 weeks than adults who do not prefer medication. The results will enlighten us to which, if any, instrument, is useful for measuring preference for treatment with anti-cholinergic medication in adults with OAB. Specific Aim 3: To use the newly validated instruments to measure the impact of preference for medication on domains related to falls (physical activity, urinary symptoms, neurocognitive testing) in older adults undergoing treatment with anti-cholinergic medications for overactive bladder. We hypothesize that adults with preference for medications will have greater improvement in physical activity and urinary symptoms, and no difference in neurocognitive testing, than women who do not have preference for medications. This aim will establish if the new instruments are useful in measuring outcomes of preference and physical activity in the clinical setting and also provide preliminary data on the impact of treatment preference and anti-cholinergic medications on physical activity and falls risk in older adults with overactive bladder.

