(OAB), a condition characterized by urgency to urinate.¹ Overactive bladder is commonly associated with urgency urinary incontinence (UUI), and older adults with UUI are at twofold higher risk for falls. UUI is increasingly being recognized as a marker for musculoskeletal weakness.^{2, 3} According to the bio-psycho-ecological paradigm,^{4, 5} falls associated with overactive bladder are a combined result of the interaction between three elements: bladder urgency; mental abilities including anxiety and embarrassment related to bladder urgency; and physical difficulty in reaching the toilet in a timely fashion. Anti-muscarinic medications are the most common class of medication used for the treatment of UUI. Six main anti-muscarinic medications are available in the United States, with similar efficacy (Qaseem 2014, AUA/SUFU OAB guidelines), and are generally prescribed based on insurance coverage as well as tolerance of side effect profile. These medications are known to improve at least two of these domains: bladder urgency,⁶ and mental anxiety related to urinary incontinence.⁷ Prior studies also suggest that reduction of bladder urgency with medications may improve ability to reach the toilet by improving physical ability, which is the third domain associated with falls. In an abstract presented at AUGS 2014, we have shown that treatment of overactive bladder in adults (mean age 61.0 ± 13.8) with fesoterodine was associated with improved physical activity as measured by the two physical activity questions of the SF-12.⁸ Several studies have reported that treatment of overactive bladder is associated with improvement in physical activity related to travel, transportation, and planning to locate restrooms.^{9, 10, 11} While these activities do not necessarily correlate with physical activities known to reduce the risk of falls e.g. walking, climbing stairs, or participating in sports these studies provide promising evidence that treatment of OAB with anti-cholinergic medications could potentially reduce falls. However, though several physical activity questionnaires exist, none have been validated in older adults with urgency urinary incontinence. Finally, anti-cholinergic medications have been implicated in neurocognitive changes that could potentially increase the risk of falls.¹² Therefore, there remains a key gap in knowledge regarding the effect of anti-cholinergic medications on physical activity and neurocognitive testing in older adults with urgency urinary incontinence. The efficacy of medications is closely related to adherence. Despite multiple benefits from anti-cholinergic treatment, the estimated adherence to anti-cholinergic medication is less than 10% at one year.¹³ Poor adherence carries the potential for wasted health care resources and continued suffering for patients. There is a lack of knowledge on how to best identify patients who will be adherent to anti-cholinergic treatment, and therefore derive the most benefit from medication. Recent studies in other conditions such as depression suggest that a key indicator for adherence is patient-expressed preference for treatment. We have previously shown that the health belief model is valid in women with OAB; women who believe in the intrinsic harm of medications have significantly worse adherence than those who believe in the benefit of medications.¹⁴ Urgency urinary incontinence is associated with increased risk of falls in older adults: Falls in the elderly have severe life-threatening consequences including injuries, immobility, and mortality.¹⁵ Several systematic reviews have confirmed that urgency urinary incontinence is an independent risk factor for falls.^{16, 17, 18} Gosch et al found that amongst patients admitted for fragility fractures, those with urinary incontinence displayed increased rates of cognitive dysfunction and depression compared to those without incontinence. Patients with incontinence were more likely to have musculoskeletal complaints that inhibit mobility, including lower back pain, weaker grip strength, and slower walking velocity.² Despite the close relationship between UUI and falls, studies that determine if treatment of UUI can reduce fall risk are lacking. Improvement in physical activity can reduce the risk of falls in older adults: Women with UUI exhibit avoidance of physical exercise.^{20, 21, 22} One of the major risk factors for falls is decline in physical functioning, which is accelerated by lack of physical activity. In a meta-analysis of 30 studies, decline in lower extremity strength was associated with falls (odds ratio 1.76, 95% CI 1.3-2.4).²³ On the other hand, improvement in physical activity by strength and balance training or simply by increased physical activity is effective in reducing fear of falling as well as actual falls.^{24, 25} The Nurses Health Study prospectively showed that older women who remained physically active longer were less likely to report the development of new onset UUI.²⁶ However, it is not known if treatment of UUI can improve physical activity in older adults. Anti-cholinergic medications may improve physical activity in older adults with urgency urinary incontinence: Prior studies suggest that treatment of overactive bladder with anti-cholinergic medications is associated with improvement in physical activity associated with quality of life.^{9, 10, 27, 28} In these studies, activity was measured using the Physical Limitations domain of the Kings Health Questionnaire (KHQ) or the Coping score of the Overactive Bladder Questionnaire (OAB-q). However, these domains examine social-related activities such as planning for travel/transportation and locating of convenient restrooms, and are therefore quality-of-life rather than physical activity measures. This may not reflect change in actual physical activity such as walking, climbing stairs, or participating in sports. Data from our preliminary study at Penn presented at AUGS/IUGA 2014 suggest that treatment with fesoterodine, in combination with behavior modification and Kegel exercises, improves women's

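### The responsiveness and discriminant-validity analyses of IPAQ and CHAMPS are not anchored to accelerometer change, so a low or high standardized response mean cannot be credited to the instrument alone

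*Combined protocol and SAP*

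**What the plan says.** Aim 1 (Objectives) covers construct validity and responsiveness of the activity questionnaires: "We will measure responsiveness of the instruments by comparing change in physical activity levels before and after treatment of OAB". The Analysis Plan for Aims 1 and 2 sets out four pieces.

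- **Concurrent validity.** IPAQ and CHAMPS are compared with the accelerometer at baseline, by Spearman and intraclass correlation.
- **Discriminant validity.** This is determined by "comparing mean differences in energy expenditure for each physical activity instrument between responders and non-responders to anticholinergic medication as defined by the PGI-I"; the comparison is made "between responders and non-responders using Wilcoxon rank sum test".
- **Responsiveness.** First, "pretreatment energy expenditure and preference will be compared with post-treatment activity and preference scores, respectively, using the t-test". Then "effect size (change in mean score/SD of baseline) and standardized response mean (change in mean score/SD of the change) will be assessed", with verbal grades that start at 0.5 for moderate.
- **Minimum clinically important difference (MCID).** This is the "mean change in energy expenditure in subjects indicating a little better or greater in the global rating scale".

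The Design and Procedures sections call the accelerometer the gold standard. They have it worn in the week after the baseline visit, before drug starts, and again in the week before the 8-week visit. The Background states: "However, it is not known if treatment of UUI can improve physical activity in older adults". Aim 3 then examines change in activity under treatment and relies on the instruments validated in Aims 1 and 2.

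**The concern.** Effect size and SRM describe how far the mean score moved. They measure an instrument's quality only if true activity is known to have moved, and by how much. Here that is an open question which the same study sets out to examine.

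Two errors are possible. If activity does not change, an accurate questionnaire has an SRM near zero and looks unresponsive. If subjects on open-label drug report more activity without moving more, an inaccurate questionnaire can earn a favourable grade. The PGI-I contrast has a related weakness: it separates groups only if symptom response goes with activity, and both sides of the comparison are self-reported.

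The study collects what is needed to tell these cases apart, namely objective activity at both time points, but no stated analysis sets questionnaire change against accelerometer change. At stake is Aim 1's answer on which instrument, if any, is useful for measuring change, and Aim 3's use of that instrument.

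**Working it through.** **1. The plan's own figure.** Under Accrual, 68 evaluable subjects give 90% power for a correlation of 0.72 against a null of 0.5. With Fisher's z, n = [(z_alpha + z_power)/(atanh 0.72 − atanh 0.50)]² + 3, where atanh 0.72 = 0.9076 and atanh 0.50 = 0.5493.

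- One-sided 0.05: [(1.645 + 1.282)/0.3583]² + 3 = 69.7, so 70. Power at 68 is 89.3%.
- Two-sided 0.05: 84.8, so 85. Power at 68 is 82.4%.
- Dropout: 68/0.85 = 80.

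The stated 68 is reproduced closely with one-sided 0.05; the plan gives no alpha or sidedness for Aim 1. The powered quantity is a questionnaire–accelerometer correlation, and the Analysis Plan computes that correlation at baseline. The sample size therefore says nothing about tracking change.

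**2. SRM mixes instrument and treatment.** Assumed model: true activity has SD 1 at each visit, correlation s = 0.6 between visits, and mean shift m. The questionnaire has correlation c with true activity and errors independent between visits. Then expected SRM ≈ c·m/√[2(1 − c²s)]. Simulated means at n = 68, with accelerometer–truth correlation 0.95 and PGI-I unrelated to activity:

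| c | SRM, m = 0 | SRM, m = 0.5 | Baseline correlation with accelerometer | Change correlation with accelerometer |
|---|---|---|---|---|
| 0.99 | 0 | 0.55 | 0.94 | 0.86 |
| 0.76 | 0 | 0.34 | 0.72 | 0.53 |
| 0.30 | 0 | 0.11 | 0.28 | 0.17 |

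With no true change, all three questionnaires have SRM about 0, none reaches 0.5, and the Wilcoxon comparison of change by responder status rejects in only 4–5% of trials. The planned responsiveness and discriminant results cannot rank them. The baseline correlation and the change correlation both can.

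**3. Reporting drift.** Assume no true change, and self-report that drifts up by d SDs of change, unrelated to the accelerometer. SRM ≥ 0.5 is the same as t ≥ 0.5·√68 = 4.12, where t is noncentral with 67 df and noncentrality d·√68.

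| d (assumed) | P(SRM ≥ 0.5) |
|---|---|
| 0.2 | 1% |
| 0.3 | 6% |
| 0.4 | 22% |
| 0.5 | 51% |
| 0.6 | 79% |

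The documents give no value for d, so the range is the result.

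**4. What a change-versus-change analysis would deliver.** Let a be the accelerometer's correlation with true activity, and fix c·a = 0.72 at baseline. Then the change correlation = c·a·(1 − s)/√[(1 − c²s)(1 − a²s)].

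- a = 0.90, c = 0.80, s = 0.8: 0.144/√(0.488 × 0.352) = 0.35.
- a = 0.95, c = 0.758, s = 0.5: 0.360/√(0.713 × 0.549) = 0.58.

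The 95% interval is tanh(atanh r ± 1.96/√65), a half-width of 0.243 on the z scale. For r = 0.35 it is 0.12 to 0.54; for r = 0.58 it is 0.40 to 0.72. This is the Pearson approximation, and Spearman intervals are slightly wider.

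**The case against.** The strongest reply is that Aim 1 does not rest on these analyses alone. Concurrent validity is assessed before any drug is taken, does not depend on a treatment effect, and is the component that was powered. The table above shows it separates good from poor questionnaires even when nothing changes. This stands. A reader might infer that Aim 1 cannot tell a poor instrument from an ineffective treatment at all; the baseline comparison rules that reading out. It does not show, however, that an instrument follows change within a person.

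Three further points stand in part.

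- The plan defines responsiveness as detecting clinically meaningful change, and a patient global rating is a coherent anchor for that. The MCID is therefore a real anchor, but a self-reported one, and it does not supply the missing accelerometer link.
- A reader might infer that both properties are judged by drug response. The split "between responders and non-responders to anticholinergic medication as defined by the PGI-I" applies to discriminant validity only; responsiveness uses pre/post change.
- The PGI-I contrast was not arbitrary. The team's earlier 8-week fesoterodine study found no activity restriction in 52% of responders against 33% of non-responders. Those were self-reported SF-12 items, so they support the choice without settling it.

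The accelerometer is also imperfect: the Background lists non-compliance and weakness for aquatic and static exercise. And the plan's wording could be read to include the accelerometer among the instruments compared before and after treatment. Even so, no analysis links the two changes in the same subject.

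**Conclusion.** The concern holds as a gap in the planned analysis. Responsiveness and discriminant validity are not anchored to accelerometer change, so a low SRM cannot be put down to the instrument rather than to absence of true change, and a high one may be drift. The size of the second risk depends on an unknown: about 6% to 79% for drifts of 0.3 to 0.6 SD of change, with 68 completers and no true change.

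A reader might go on to infer that the stated grades would reverse Aim 1's answer on which instrument is useful. The documents do not support that, because no rule lets SRM override concurrent validity. Nor is this a design that cannot answer the question, since the data are collected at both visits. The projected change correlation of 0.35 to 0.58 assumes a baseline correlation of 0.72, errors independent between visits, accelerometer–truth correlation of 0.90 to 0.95, and true-activity stability of 0.8 to 0.5.

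**What to change.** In the Analysis Plan, under responsiveness for Aim 1:

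- Add the Spearman correlation, with 95% confidence interval, between week-8-minus-baseline change in each of IPAQ and CHAMPS and the accelerometer change in the same subjects.
- Report the accelerometer's own effect size and SRM, and interpret those of the questionnaires beside them. State that no instrument will be graded on SRM alone.
- Keep the PGI-I contrast and the MCID. State that the PGI-I contrast is informative about an instrument only to the extent that treatment affects activity.

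Accelerometer-defined groups for discriminant validity are not needed; they would largely repeat the planned baseline correlation in coarser form.

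The cost is a few sentences and a little extra analysis, with no new data collection. The downside is moderate precision: with 68 completers, the interval around a change correlation of 0.35 to 0.58 is roughly 0.3 to 0.4 wide.
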